4.3.1 Remote Consultation for Remote Video plus Coaching

BHS will receive a study-purchased audio recorder to use to record the student groups. They will be instructed to upload the recording to OneDrive. Research team consultants will provide synchronous consultation to BHS in the RV+ condition via Webex. The consultation will have two main components: (a) session preparation (CPP/CATS) or review and planning (CICO) and (b) coaching.

Session Preparation: Session preparation for CPP and CATS will consist of (a) discussing referrals to the groups; (b) conducting a step-by-step walkthrough of the session objectives, (c) reviewing the CBT principles behind the treatment components for that session; (d) encouraging adherence and the use of active learning strategies; (e) problem-solving barriers to implementation and helping implementers reflect on past challenges (e.g., attendance problems, organizational barriers, materials/resources) in order to successfully implement the next session with appropriate adaptations as needed; and (f) enhancing BHS's use of empathy and positive reinforcement through modeling. Research consultants for CICO will (a) review the school's CICO implementation manual and (b) provide feedback and suggestions for program implementation.

Coaching: Coaching for CPP and CATS will consist of (a) goal setting,⁶⁵ (b) self-reflection,⁶⁶ and (c) performance feedback.⁶⁷ BHS will be told that they are expected to reach high fidelity when implementing the intervention. Then, implementers will be asked to reflect on the previous session (e.g., "How do you think you did during the last CPP/CATS session? What do you think went right? What do you think did not go well?"). Finally, the consultant will use audio clips from the previous session that contain examples of well-executed implementation objectives and brief audio clips that contain ineffective or less than optimal execution of objectives. The consultant will also discuss how the implementer handled student behavior in session, including overall level of participation and enthusiasm, and disruptive or withdrawn behavior. The audio clips will be contained in a OneDrive server uploaded by implementers. All consultation procedures will be detailed in a consultation manual. Coaching for CICO will consist of (a) providing performance feedback to the CICO coordinator and data analyst about their program (e.g., use of data to refer students to CICO, student progress monitoring) and (b) problem solving implementation barriers.

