3.1.1 Pre-Trial Activities and Screening Phase

The Remote Training Strategy was developed during Phase 1 of this 5-year project using an iterative process (*Rapid Prototyping*) to develop the appropriateness, feasibility, acceptability and preliminary efficacy of the online training platform.

School Selection: The National Center for Education Statistics (NCES) subdivides rural and town school areas by their proximity to an urbanized area into fringe, distant, or remote locations.⁴⁷ Participant schools will be located in any of these three rural locations or town, remote area and/or the school will serve rural communities. We will invite 24 schools representing the 2 geographic locations (urban/rural) to participate in the pilot efficacy study. After receiving school approval to participate schools will be stratified based on the geographic location and a computer-generated block randomization list will be prepared to randomize the 24 schools in a 1:1:1 ratio to either RV, RV+ or CC (8 schools/arm) stratified by geographic locations (urban/rural). The block randomization with varying will ensure ensure equal number of schools in each arm and eliminate the predictability of schools' assignment.

Behavioral Health Staff Screening: Recruitment will begin with assistance from the school principal who may nominate school behavioral health staff to participate in the study. Additionally, the research staff will reach out to school behavioral health staff concurrently with the school principal. The research staff will speak with school staff by phone or via WebEx to clearly explain study procedures, as well as potential risks and benefits. BHS will be clearly informed of the voluntary nature of their participation and will receive ample opportunities to ask questions. A copy of the consent form will be provided to the BHS, and consent will be obtained electronically via REDCap.

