Student Screening: Recruitment of child participants will begin with research staff assisting school behavioral health staff who will examine teacher nomination data for students in specific grades and classes in order to identify students for Tier 2 interventions. We will train BHS remotely on providing a brief in-service training to teachers tasked with nominating students on recognizing warning signs of excessive anxiety, depression, and disruptive behavior problems in children, and completing the screening measures. Following the remote training, BHS will ask teachers from specific grades or classes to nominate students. **First**, teachers will be asked to rank order students and then select the top three students with externalizing problems and the top three students with internalizing problems. **Second**, parents and teachers will complete the SDQ (paper or electronically) on these identified students. **Third**, parents and teachers will give the SDQ forms to the BHS member (when applicable). **Fourth**, BHS will scan the SDQ to CHOP staff to score. **Fifth**, students who score above the specified cut-off on the externalizing or internalizing dimension will be selected for the next step, which will require BHS to contact the parents and request that they complete the SCARED or to ask a teacher of the student to complete the SAEBRS. **Sixth**, children who score at least 25 or there is an elevated subscale for the SCARED or if the student score on the Social Behavioral subscale of the SAEBRS is 12 or less, they will be considered for participation in one of the groups or in CI/CO. **The research aspect of the project will begin at this point.** Children who meet inclusion criteria will be invited to participate in the study. Research staff will ask parents to provide consent for their child to participate in the intervention. The children will also be asked to provide assent to participate in the intervention. Informed consent (parent) and assent (child) will be obtained by research staff prior to enrollment. Participating BHS will facilitate consent meetings with eligible children and their parents. A research staff member will join these meetings by phone or via a videoconference.

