4.2.2 Guided Video for Remote Video and Remote Video plus Coaching

Following the initial training workshop and after BHS have identified students for interventions, BHS in the RV and RV+ conditions will be given access to the training videos. The videos will be made available through CHOP OPEN that has the ability to measure how many times each video has been accessed by the BHS and for how long. Each participant will be given access to the videos that correspond to the interventions that they plan to use. All Tier 2 implementers in RV and RV+ will be given access to videos that address general topics (e.g., how to use data to identify students for participation; dealing with implementation barriers).

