6.2 Statistical Analysis

Prior to statistical comparison between groups (RV, RV+, and CC), all pertinent variables collected for the pilot study will be reported by groups and presented as mean, standard deviation, median, minimum, maximum and the 95% confidence intervals for continuous variables, while frequencies and proportions will be used for categorical variables. Continuous data measures will also be checked for normality and outliers. Non-normally distributed continuous data variables will be examined and transformed "normalized" if needed using appropriate transformation functions. Outliers not found to be in error will be kept in the analysis. Since the school is the randomization unit, BHS and student characteristics (Demographic and other potential confounders will be compared between the two groups using the two independent samples t-test or the non-parametric Wilcoxon signed rank test) to identify pre-treatment differences between the two groups. If the two groups are found to be statistically different in a pre-measured outcome, the pre-measurement(s) will be included in the subsequent analyses as a covariate using analysis of covariance (ANCOVA).

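### Students are recruited after schools are randomised, and no rule hides the arm or closes the student list first, so the student groups can differ by arm

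*Combined protocol and SAP*

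**What the plan says.** **Randomisation.** Section 6.2 opens its comparison with "Since the school is the randomization unit". Section 3.1.1 gives the timing: "After receiving school approval to participate schools will be stratified based on the geographic location and a computer-generated block randomization list will be prepared". Section 8.1.1 repeats the scheme. Neither section ties allocation to the completion of student enrolment.

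**Student recruitment.** Section 3.1.2 trains staff of every condition on referral and screening. Section 3.1.1 places teacher nomination after that training, and section 4.3 lets the behavioral health staff (BHS) choose which grade group to screen. Screening and consent follow: "Participating BHS will facilitate consent meetings with eligible children and their parents". Research staff obtain the consent and assent themselves (sections 3.1.1 and 8.6.3).

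**Referral content by arm.** In RV+ only, section 4.3.1 says "Session preparation for CPP and CATS will consist of (a) discussing referrals to the groups", among other items, and lists CI/CO performance feedback that covers "use of data to refer students to CICO". The RV and RV+ videos include a general topic on "how to use data to identify students for participation" (section 4.2.2).

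**The one sequencing rule.** Section 4.2.2 states that, following the initial workshop and "after BHS have identified students for interventions, BHS in the RV and RV+ conditions will be given access to the training videos".

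**Analysis.** Section 6.3 compares pre/post change scores and fits an arm-by-time model. Section 6.2 adds the baseline value as a covariate only where a baseline test is significant. It describes that test for two groups, although the trial has three arms.

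**The concern.** Randomising schools makes the schools comparable. It makes the students comparable only if the arm cannot affect which students enter. Here students enter after allocation, through people who may know the arm, and in one arm the support package itself deals with referral. If RV+ schools put forward students who differ in severity, fit to the programme or family engagement, part of any difference in student change would reflect who was recruited rather than how staff were trained.

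The student outcomes are primary endpoints (section 6.1). The pilot is meant to estimate effect sizes (section 6.4) and to supply estimates for a larger study (section 6.3). A recruitment difference would carry into those estimates.

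**Working it through.** **1. Order of events.** No single sentence gives the whole sequence, so it has to be assembled: school approval, then the randomisation list (3.1.1, 8.1.1); common training, with conditions already named (3.1.2); grade choice, nomination, screening and consent (4.3, 3.1.1). No section places student enrolment before allocation. No section says that BHS, teachers or consenting staff are unaware of the arm. Section 8.7 pays BHS an amount that varies with the arm and partly covers screening, which suggests, without proving, that they know it.

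**2. What differs by arm in relation to student entry.**

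| | CC | RV | RV+ |
|---|---|---|---|
| Common referral and screening training | yes | yes | yes |
| Video on identifying students | no | yes, after identification | yes, after identification |
| Discussion of group referrals | no | no | yes, timing not stated |
| Feedback on CI/CO referral | no | no | yes, timing not stated |

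The video rule is keyed to identification, not to consent or completed baseline measures.

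**3. How much of the sample the CI/CO route covers.** The abstract has 5 group students per school plus two CI/CO staff with 4 students each: 8 of 13, or 62%. Sections 3.2.1 and 4.3 give 144 of 288, or 50%. The counts disagree, but either way it is at least half.

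**4. The plan's own margin.** Inputs from section 6.4: 89 evaluable students per arm, SD of change 8. Half-width = t(0.975, 176) × 8 × √(2/89) = 2.37, against a stated 2.4. The figure reproduces and is not disputed. It covers sampling variation only, with no allowance for differential recruitment.

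**5. Whether the baseline test would catch an imbalance.** Inputs: 104 students per arm (6.4) and 13 per school (8.1.1). Assumptions, because the documents give no values: imbalance of 0.2, 0.3 or 0.5 baseline SD; two-sided 5% test; intraclass correlation (ICC) 0 to 0.10.

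Power ≈ Φ(d√(n/2) − 1.96), with n = 104 divided by the design effect 1 + (13 − 1) × ICC.

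- ICC 0, n = 104: d = 0.2 gives Φ(1.442 − 1.96) = 0.30; d = 0.3 gives Φ(2.163 − 1.96) = 0.58; d = 0.5 gives 0.95.
- ICC 0.05, design effect 1.6, n = 65: 0.21, 0.40 and 0.81.
- ICC 0.10, design effect 2.2, n = 47.3: 0.16, 0.31 and 0.68.

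The last two rows are for a test that allows for clustering. The t-test in section 6.2 does not. With clustered data it would also reject too often when the arms do not differ systematically, so it is a poor trigger in both directions. A large imbalance would usually be seen; one of 0.2 to 0.3 SD would often be missed.

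**The case against.** **Safeguards exist.** All arms receive the same training. Teachers nominate the three highest-ranked students of each problem type, the SDQ is scored centrally against a cut-off, SCARED and SAEBRS thresholds follow, and research staff take consent. This stands, and it limits how far eligibility can drift. It does not fix which grade is screened, which eligible students are put forward or which families agree, and mean severity above a threshold can still differ.

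**The referral text is thin.** A reader might infer that RV+ consultants choose the students, or advise before consent. The documents do not say so. The group item sits in the implementation phase, within preparation for sessions, and the CI/CO item is feedback on a programme already in place. Details are left to a consultation manual that is not included. What remains is that timing is unstated and CI/CO referral could be ongoing.

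**The video route is mostly closed.** Section 4.2.2 delays access until students are identified. That stands. It sits awkwardly with a video on how to identify them.

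**Analysis can help.** A reader might infer that the problem cannot be repaired in analysis, or might put a figure on regression to the mean as a share of the 2.4 margin. Neither is supported. Unconditional baseline adjustment largely removes bias from measured baseline differences. A numerical bias needs a baseline gap and a pre/post correlation that the documents do not give. The usual formula also assumes selection on the outcome score, whereas selection here uses teacher ranking, SDQ, SCARED and SAEBRS, and the outcomes are BASC-3 and engagement scales.

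**It is a pilot.** Section 6.4 disclaims power for hypothesis tests. That lowers the stakes of any p-value, but not of a biased effect estimate passed to a later trial.

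**Conclusion.** The gap is real and should be closed. Students enter after allocation, nothing conceals the arm from those who bring them in, and referral is part of the support in one arm only. The student groups can differ by arm. The documents do not show that they will, or in which direction, and the size is not estimable from them. The concern is with the student endpoints.

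The conclusion rests on an order of events assembled from several sections, none of which contradicts it, and on the absence of any concealment or closed-cohort rule. The finding that the baseline test is a weak trigger rests on the assumed imbalances and ICCs shown above.

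Baseline adjustment deals with measured differences; only a change of sequence protects against unmeasured ones.

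**What to change.** 1. Extend the sequence that section 4.2.2 already applies to videos. In each school, complete nomination, screening, consent, assent and baseline measures before the arm is disclosed there and before any video access or RV+ consultation. Limit the main student analysis to that cohort, and start RV+ discussion of referrals only after it closes. Later referrals may still receive the programme.
2. In sections 6.2 and 6.3, adjust every student outcome for its baseline value in all three arms, and drop the significance-test trigger.
3. Report the numbers nominated, screened, eligible and consented by arm.

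**Cost.** Items 2 and 3 are close to free. Item 1 brings a modest delay before videos and coaching start; section 8.4.2 lists a wait of up to two months before intervention as a participant risk, so the delay should be kept short. BHS consent and payment wording must not reveal the assigned arm, which matters because section 8.7 varies payment by arm. Late referrals are lost to the main student analysis. The number of schools does not change, and the RV+ content changes only in when referral discussion begins.

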4.4 Subject Completion/Withdrawal

Subjects may withdraw from the study at any time without prejudice to their care, education or employment. They may also be discontinued from the study at the discretion of the Investigator for lack of adherence to the study and/or development of exclusionary criteria. Student participants will be removed from the study if they develop exclusionary criteria during the trial or if it is determined that the intervention group is not age/developmentally appropriate based on the grade level of the majority of enrolled students. It will be documented whether or not each subject completes the clinical study. If the Investigator becomes aware of any serious, related adverse events after the subject completes or withdraws from the study, they will be recorded in the study files.

5 STUDY EVALUATIONS AND MEASUREMENTS

5.1 Screening Measures

Screening for Tier 2: The Strengths and Difficulties Questionnaire plus Impact Supplement (SDQ).⁵⁴ The SDQ is a 25-item, 3-point scale questionnaire used to assess the psychological adjustment of children and youth, ages 4-17. ⁵⁴ The SDQ has excellent psychometric properties as a screening instrument for behavioral and emotional problems. ⁵⁴ We will use the scores on the Conduct Problems and Emotional Problems ⁶² scales plus impact supplement scores (impairment) for screening students for Tier 2.

The Screener for Child Anxiety Related Disorders (SCARED): is a 41-item questionnaire used to screen for children with anxiety disorders, using five sub-scales and a Total Score. It has excellent psychometric properties and has been used in community settings as a screening instrument for anxiety disorders.

The Social, Academic, and Emotional of Behavioral Risk Screener (SAEBRS): is a 19-item, psychometrically sound screening instrument for assessing emotional and behavioral risk. The SAEBSR is completed by school staff using a 4-point Likert scale. We will use the “Social Behavior” subscale of the SAEBSR to determine eligibility for CPP and CICO.

5.2 Demographic Information

Demographic information for students will be collected at baseline from a parent. Demographic information for BHS will be collected via a REDCap survey following consent to participate.

Demographic information for administrators will be collected via a REDCap survey following consent to participate.

5.3 Implementation Fidelity

Content Fidelity to Tier 2 Group CBT (CPP & CATS). The Content Fidelity Checklist (CFC) reflects each activity component of the session agenda of the treatment protocols. Raters use a yes/no response scale to indicate whether or not the implementer covered a particular component. All GCBT sessions will be audio-recorded. 100% of sessions will be

coded by the first coder and approximately 20% of sessions will be randomly selected and coded by the second coder. Interrater reliability will be evaluated using Kappa coefficients⁶⁹

Process Fidelity to Tier 2 Group CBT (CPP & CATS). Process fidelity will be assessed via an adapted version of the rating system developed by Lochman and colleagues.⁷⁰ Ten items are rated on a scale of 0 to 4, with 0 being "Not At All" and 4 being "Very Often". Ratings are given on the extent to which school staff members delivered the intervention in an orderly fashion, using active learning strategies, etc. Exploratory factor analysis (EFA) yielded two factors on the 10-item scale. We will use the average *Total* and factor scores for analysis. 100% of sessions will be coded by the first coder and approximately 20% of sessions will be coded by the second coder. Interrater reliability will be evaluated using ICC.

Content Fidelity for CI/CO. Content fidelity for CI/CO will be assessed via the CI/CO Implementation Guide Fidelity Checklist (IGFC). The CI/CO IGFC is completed by the consultant (research staff) after school teams submit their completed CI/CO Implementation Guide. The IGFC is completed once and measures both the content and quality of the customized manual components for each school. The CI/CO IGFC/Content Measure is a 26-item measure of CI/CO customization of the following CI/CO components: (a) staff roles and responsibilities, (b) CI/CO process logistics, (c) daily progress report, (d) motivation system, (e) fading and self-monitoring procedures, (f) staff training procedures, and (g) data collection and progress monitoring procedures. Each item is scored according to completion status as "yes," "no," or "not applicable." The CI/CO IGFC/Content Measure will be scored by recording the frequency of "yes" scores over the frequency of "yes," and "no" scores.

The CI/CO IGFC/Quality Measure, or part 2 of the IGFC/Content Measure, is also completed by the consultant (research staff) once teams submit their completed CI/CO Implementation Guide. The IGFC/Quality Measure is a 14-item measure of the quality of, or degree to which, team responses in customizing their respective CI/CO Implementation Guides are comprehensive, clear, feasible. Measurement entails examining team responses to items related to the (a) implementation roles and responsibilities, (b) implementation process, (c) motivation system, (d) fading and self-monitoring, (e) training/orientation of staff, mentors, students and families, and (f) data entry and progress monitoring. The IGFC/Quality Measure will be scored by recording a score of 0-3 for each item depending on whether or not the team response meets the criteria for being comprehensive, clear, and feasible (with 1 point awarded for each).

Process Fidelity to CI/CO. Process fidelity for CI/CO will be assessed with the Check-In/Check-Out Fidelity Checklist, a measure of the daily implementation of CI/CO. The CI/CO Fidelity Checklist is completed by the consultant (research staff) on a monthly basis after collecting the completed Daily Progress Report (DPR) student forms for each student involved in CICO. The Check-in/Check-Out Fidelity Checklist is an 11-item form that indicates whether or not students received daily CICO feedback based on the occurrence of the following: (a) student identification, (b) feedback date, (c) recorded goal, (d) behavioral expectations rated by the teacher for each period, (e) the number of daily points earned out of the number of possible points, (f) an indication of whether or not the goal was met, and (g) the signature of the teacher/mentor. The 11 items will be scored as "occurred" or "did not occur." The Check-In/Check-Out Fidelity Checklist will be scored by recording occurrence over occurrence-plus-non-occurrence and multiplying the decimal by 100.

Adoption Inventory (AI). The AI will track the number of times each intervention is used per school, per condition. This information will be collected one time at the end of the intervention via a REDCap survey.

Dosage Inventory (DI). The DI is an Excel tracking sheet exported from the website hosting the video modules listing the number of times and length of time each video module is accessed by BHS.

Penetration Inventory (PI). The PI will list EBP penetration at the student level (students receiving EBPs at Tier 2). This information will be collected one time at the end of the intervention via a REDCap survey.

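### Section 5.3 lets the consultant role that coaches RV+ schools also score their CI/CO fidelity, with no independent rater, masking or double scoring specified

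*Combined protocol and SAP*

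**What the plan says.** Section 6.1 makes content and process fidelity the primary endpoints for school staff.

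Section 5.3 names the scorer of each CI/CO measure:

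- Content (26 completion items): "The CI/CO IGFC is completed by the consultant (research staff) after school teams submit their completed CI/CO Implementation Guide".
- Quality (14 items, each 0 to 3): this part "is also completed by the consultant (research staff) once teams submit their completed CI/CO Implementation Guide".
- Process (11 items, taken from the daily report forms): "The CI/CO Fidelity Checklist is completed by the consultant (research staff) on a monthly basis".

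Section 4.3.1, whose heading limits it to Remote Video plus Coaching, says that consultants "provide synchronous consultation to BHS in the RV+ condition via Webex". For CI/CO they review the school's "CICO implementation manual and (b) provide feedback and suggestions for program implementation". It adds: "Coaching for CICO will consist of (a) providing performance feedback to the CICO coordinator and data analyst about their program".

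For the group programmes (CPP and CATS), Section 5.3 has a first coder for all sessions and a second coder for a sample. For process fidelity it says "approximately 20% of sessions will be coded by the second coder". Agreement is reported by kappa for content and by ICC for process. No CI/CO measure has a second rater or an agreement statistic. The documents state no masking of raters to arm for any fidelity measure.

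**The concern.** The role that supports RV+ schools on CI/CO is the role that scores CI/CO fidelity in every school. Control and RV schools receive no CI/CO manual review or coaching under Section 4.3.1. If a coach is lenient toward schools he or she has worked with, the leniency arises in one arm only. It would then shift the RV+ contrast instead of adding noise to all arms, and with one rater and no agreement check nothing in the data would reveal it.

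CI/CO is a large part of the endpoint. Sections 3.1 and 4.3 require every school to use it, and Section 3.2.1 expects two of the three staff per school to deliver it: 2 × 24 = 48 of 72. The trial is a pilot whose purpose, in Section 6.4, is to estimate effect sizes, and Section 6.3 intends estimates for a larger study. A biased point estimate would carry into that planning whether or not any test is significant.

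**Working it through.** **1. Overlap of roles.** Setting Sections 4.3.1 and 5.3 side by side:

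| CI/CO measure | Scorer named in 5.3 | Nature of the score | Second rater |
|---|---|---|---|
| Guide content, 26 items | consultant | yes / no / not applicable, once per school | none stated |
| Guide quality, 14 items | consultant | 0–3 judgement: comprehensive, clear, feasible | none stated |
| Process checklist, 11 items | consultant, monthly | whether entries appear on daily forms | none stated |

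Section 5.3 describes the guide score as covering the components of each school's customized manual. Section 4.3.1 has RV+ consultants review the school's CI/CO manual. These appear to be the same document, though the plan calls it a guide in one place and a manual in the other.

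**2. The plan's own precision figure.** Inputs from Section 6.4: 24 staff per arm, SD 16 for content fidelity, two-sided 95% interval.

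Half-width = t(0.975, 2n−2) × SD × √(2/n) = 2.013 × 16 × √(2/24) = 9.30. The stated 9.3 is reproduced. For process fidelity (SD 0.6) the same formula gives 0.349, against the stated 0.35.

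**3. The figure that fits the guide score.** The guide is scored once per school, and Section 3.2.1 gives 8 schools per arm. Keeping SD 16 (an assumption, since no SD specific to this measure is given):

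Half-width = t(0.975, 14) × 16 × √(2/8) = 2.145 × 16 × 0.5 = 17.2.

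**4. Scale of one item.** The content score is the yes count divided by yes plus no. With no item marked not applicable, one item is 100/26 = 3.8 points, two are 7.7 and three are 11.5.

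**5. Illustration only.** Suppose there is no true difference and every RV+ school is scored one, two or three items too high. These leniency values are assumed; the documents give none. The mean difference is shifted by the full 3.8, 7.7 or 11.5 points. With 8 schools per arm and SD 16, the standard error is 16 × √(2/8) = 8. The chance that a 95% interval excludes zero, from the noncentral t with 14 degrees of freedom, is then about 7%, 15% or 27%, where it should be 5%.

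**6. Which measure is most exposed.** The quality rating asks for judgement on each item and carries the greatest risk. The 26 completion items are checked against a written document and leave less room. The monthly checklist records whether fields on the daily forms were filled in, which is largely clerical, so its risk is least.

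**The case against.** The strongest reply is that the documents describe a role and do not identify individuals. The guide is scored in all 24 schools, including control and RV schools that have no coach, so the word consultant cannot mean only the school's own coach. Section 4.2.1 also has research consultants training staff in every arm. A reader might infer that the same person coaches and scores a school, unmasked and alone. The text does not say so; it only fails to prevent it. That part of the reply stands.

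The timing of the manual review is also not stated. If it follows submission, the consultant did not shape the guide that was scored. If it precedes submission, a better guide is partly a genuine effect of RV+ and not leniency. This stands too, and it means that a higher RV+ score would not in itself be evidence of bias.

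A reader might set three lenient items (11.5 points) against the 9.3 margin and conclude that leniency would exceed the trial's precision. That comparison fails: 9.3 assumes 24 scores per arm, and against 17.2 even three items fall inside the margin.

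Nor can the group-session coders be presumed independent. Section 5.3 calls them only first and second coder, and Section 8.2 refers to study team members. What group sessions have and CI/CO lacks is double coding with an agreement statistic.

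Finally, Section 6.4 says that the pilot is not powered for hypothesis tests. That lowers the weight of false-positive rates, but not of bias in the effect estimates that the pilot is meant to supply. None of these replies supplies a rule that separates coach from scorer.

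**Conclusion.** The concern holds as a gap in the scoring rule. Section 5.3 permits RV+ schools to be scored by the consultant who supports them, on measures that belong to a primary endpoint, with no masking, independent rater or second rater specified for CI/CO. This could bias the RV+ contrast. Upward is the most plausible direction, but it is an expectation and not something that the documents show.

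The size cannot be computed from the documents. The only firm scale is about 3.8 points per content item when none is not applicable, against a half-width of about 17.2 if the SD is 16 and 8 schools per arm are scored. The concern is strongest for the 14-item quality rating and weakest for the monthly checklist. It covers the CI/CO part of the fidelity endpoint only. It is worth correcting because the correction is cheap.

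**What to change.** Amend Section 5.3 as follows:

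- Each school's guide, content and quality, is scored by existing research staff who do not consult with that school, from copies with school name and arm removed where feasible. The consultant may still collect the materials.
- About 20% of guides are scored twice (0.20 × 24 = 4.8, so about 5) and agreement is reported, in line with the group sessions.
- The monthly checklist is completed by a rater who does not serve the school. Full de-identification of the daily forms is not needed: student identification and signature are themselves scored fields, and on the abstract's four students per CI/CO staff member the forms cover 2 × 4 × 24 = 192 students.
- No one scores a school that he or she coached, including for audio-recorded group sessions.

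The cost is a modest reassignment of scoring among existing staff and some redaction of 24 guides. Redaction may not fully hide a school, because each guide is customized. No intervention changes and participants carry no extra burden. If coaching and scoring are already kept apart in practice, one sentence in Section 5.3 settles that part, and the double scoring remains to be added.
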